11.22 Non-Measurable Disease

All other lesions (or sites of disease) are considered non-measurable disease, including pathological nodes (those with a short axis ≥ 1.0 to < 1.5 cm). Bone lesions, leptomeningeal disease, ascites, pleural/pericardial effusions, lymphangitis cutis/pulmonis, inflammatory breast disease, and abdominal masses (not followed by CT or MRI), are considered as non-measurable as well.

NOTE: ‘Cystic lesions’ thought to represent cystic metastases can be considered as measurable lesions, if they meet the definition of measurability described above. However, if non-cystic lesions are present in the same patient, these are preferred for selection as target lesions.

Lymph nodes that have a short axis < 1.0 cm are considered non- pathological (i.e., normal) and should not be recorded or followed.

11.3 Guidelines for Evaluation of Measurable Disease

11.31 Measurement Methods:

- All measurements should be recorded in metric notation (i.e., decimal fractions of centimeters) using a ruler or calipers.
- The same method of assessment and the same technique must be used to characterize each identified and reported lesion at baseline and during follow-up. For patients having only lesions measuring at least 1 cm to less than 2 cm must use CT imaging for both pre- and post-treatment tumor assessments.

11.32 Acceptable Modalities for Measurable Disease:

- Conventional CT and MRI: This guideline has defined measurability of lesions on CT scan based on the assumption that CT slice thickness is 5 mm or less. If CT scans have slice thickness greater than 5 mm, the minimum size for a measurable lesion should be twice the slice thickness.
- As with CT, if an MRI is performed, the technical specifications of the scanning sequences used should be optimized for the evaluation of the type and site of disease. The lesions should be measured on the same pulse sequence. Ideally, the same type of scanner should be used and the image acquisition protocol should be followed as closely as possible to prior scans. Body scans should be performed with breath-hold scanning techniques, if possible.
- PET-CT: If the site can document that the CT performed as part of a PET-CT is of identical diagnostic quality to a diagnostic CT (with IV and oral contrast), then the CT portion of the PET-CT can be used for RECIST measurements and can be used interchangeably with conventional CT in accurately measuring cancer lesions over time.
- Chest X-ray: Lesions on chest x-ray are acceptable as measurable lesions when they are clearly defined and surrounded by aerated lung. However, CT scans are preferable.
- FDG-PET: FDG-PET scanning is allowed to complement CT scanning in assessment of progressive disease [PD] and particularly possible 'new' disease. A 'positive' FDG-PET scanned lesion is defined as one which is FDG avid with an uptake greater than twice that of the surrounding tissue on the attenuation corrected image; otherwise, an FDG-PET scanned lesion is considered 'negative.' New lesions on the basis of FDG-PET imaging can be identified according to the following algorithm:
 - a. Negative FDG-PET at baseline with a positive FDG-PET at follow-up is a sign of PD based on a new lesion.
 - b. No FDG-PET at baseline and a positive FDG-PET at follow-up:
 - i. If the positive FDG-PET at follow-up corresponds to a new site of disease confirmed by CT, this is PD.
 - ii. If the positive FDG-PET at follow-up is not confirmed as a new site of disease on CT at the same evaluation, additional follow-up CT scans (i.e., additional follow-up scans at least 4 weeks later) are needed to determine if there is truly progression occurring at that site. In this situation, the date of PD will be the date of the initial abnormal FDG-PET scan.
 - iii. If the positive FDG-PET at follow-up corresponds to a pre-existing site of disease on CT that is not progressing on the basis of the anatomic images, it is not classified as PD.

11.33 Measurement at Follow-up Evaluation:

- The cytological confirmation of the neoplastic origin of any effusion that appears or worsens during treatment when the measurable tumor has met criteria for response or stable disease is mandatory to differentiate between response or stable disease (an effusion may be a side effect of the treatment) and progressive disease.
- Cytologic and histologic techniques can be used to differentiate between PR and CR in rare cases (e.g., residual lesions in tumor types such as germ cell tumors, where known residual benign tumors can remain.)

11.4 Measurement of Effect

11.41 Target Lesions & Target Lymph Nodes

- Measurable lesions (as defined in Section 11.21) up to a maximum of 5 lesions, representative of all involved organs, should be identified as “Target Lesions” and recorded and measured at baseline. These lesions can be non-nodal or nodal (as defined in 11.21), where no more than 2 lesions are from the same organ and no more than 2 malignant nodal lesions are selected.

Note: If fewer than 5 target lesions and target lymph nodes are identified (as there often will be), there is no reason to perform additional studies beyond those specified in the protocol to discover new lesions.

- Target lesions and target lymph nodes should be selected on the basis of their size, be representative of all involved sites of disease, but in addition should be those that lend themselves to reproducible repeated measurements. It may be the case that, on occasion, the largest lesion (or malignant lymph node) does not lend itself to reproducible measurements in which circumstance the next largest lesion (or malignant lymph node) which can be measured reproducibly should be selected.
- Baseline Sum of Dimensions (BSD): A sum of the longest diameter for all target lesions plus the sum of the short axis of all the target lymph nodes will be calculated and reported as the baseline sum of dimensions (BSD). The BSD will be used as reference to further characterize any objective tumor response in the measurable dimension of the disease.
- Post-Baseline Sum of the Dimensions (PBSD): A sum of the longest diameter for all target lesions plus the sum of the short axis of all the target lymph nodes will be calculated and reported as the post-baseline sum of dimensions (PBSD). If the radiologist is able to provide an actual measure for the target lesion (or target lymph node), that should be recorded, even if it is below 0.5 cm. If the target lesion (or target lymph node) is believed to be present and is faintly seen but too small to measure, a default value of 0.5 cm should be assigned. If it is the opinion of the radiologist that the target lesion or target

lymph node has likely disappeared, the measurement should be recorded as 0 cm.

- The minimum sum of the dimensions (MSD) is the minimum of the BSD and the PBSD.

11.42 Non-Target Lesions & Non-Target Lymph Nodes

Non-measurable sites of disease (Section 11.22) are classified as non-target lesions or non-target lymph nodes and should also be recorded at baseline. These lesions and lymph nodes should be followed in accord with 11.433.

11.43 Response Criteria

11.431 All target lesions and target lymph nodes followed by CT/MRI/PET-CT/Chest X-ray/physical examination must be measured on re-evaluation at evaluation times specified in Section 11.1. Specifically, a change in objective status to either a PR or CR cannot be done without re-measuring target lesions and target lymph nodes.

Note: Non-target lesions and non-target lymph nodes should be evaluated at each assessment, especially in the case of first response or confirmation of response. In selected circumstances, certain non-target organs may be evaluated less frequently. For example, bone scans may need to be repeated only when complete response is identified in target disease or when progression in bone is suspected.

11.432 Evaluation of Target Lesions

- Complete Response (CR): All of the following must be true:
 - a. Disappearance of all target lesions.
 - b. Each target lymph node must have reduction in short axis to <1.0 cm.
- Partial Response (PR): At least a 30% decrease in PBSD (sum of the longest diameter for all target lesions plus the sum of the short axis of all the target lymph nodes at current evaluation) taking as reference the BSD (*see* Section 11.41).
- Progression (PD): At least one of the following must be true:
 - a. At least one new malignant lesion, which also includes any lymph node that was normal at baseline (< 1.0 cm short axis) and increased to ≥ 1.0 cm short axis during follow-up.

- b. At least a 20% increase in PBSD (sum of the longest diameter for all target lesions plus the sum of the short axis of all the target lymph nodes at current evaluation) taking as reference the MSD (Section 11.41). In addition, the PBSD must also demonstrate an absolute increase of at least 0.5 cm from the MSD.
- c. See Section 11.32 for details in regards to the requirements for PD via FDG-PET imaging.

- Stable Disease (SD): Neither sufficient shrinkage to qualify for PR, nor sufficient increase to qualify for PD taking as reference the MSD.

11.433 Evaluation of Non-Target Lesions & Non-target Lymph Nodes

- Complete Response (CR): All of the following must be true:
 - a. Disappearance of all non-target lesions.
 - b. Each non-target lymph node must have a reduction in short axis to <1.0 cm.
- Non-CR/Non-PD: Persistence of one or more non-target lesions or non-target lymph nodes.
- Progression (PD): At least one of the following must be true:
 - a. At least one new malignant lesion, which also includes any lymph node that was normal at baseline (< 1.0 cm short axis) and increased to ≥ 1.0 cm short axis during follow-up.
 - b. Unequivocal progression of existing non-target lesions and non-target lymph nodes. (NOTE: Unequivocal progression should not normally trump target lesion and target lymph node status. It must be representative of overall disease status change.)
 - c. See Section 11.32 for details in regards to the requirements for PD via FDG-PET imaging.

11.44 Overall Objective Status

The overall objective status for an evaluation is determined by combining the patient's status on target lesions, target lymph nodes, non-target lesions, non-target lymph nodes, and new disease as defined in the following tables:

Target Lesions & Target Lymph Nodes	Non-Target Lesions & Non-Target Lymph Nodes	New Sites of Disease	Overall Objective Status
CR	CR	No	CR
CR	Non-CR/Non-PD	No	PR
PR	CR Non-CR/Non-PD	No	PR
CR/PR	Not All Evaluated*	No	PR**
SD	CR Non-CR/Non-PD Not All Evaluated*	No	SD
Not all Evaluated	CR Non-CR/Non-PD Not All Evaluated*	No	Not Evaluated (NE)
PD	Unequivocal PD CR Non-CR/Non-PD Not All Evaluated*	Yes or No	PD
CR/PR/SD/PD/Not all Evaluated	Unequivocal PD	Yes or No	PD
CR/PR/SD/PD/Not all Evaluated	CR Non-CR/Non-PD Not All Evaluated*	Yes	PD

*See Section 11.431

11.45 Symptomatic Deterioration: Patients with global deterioration of health status requiring discontinuation of treatment without objective evidence of disease progression at that time, and not either related to study treatment or other medical conditions, should be reported as PD due to “symptomatic deterioration.” Every effort should be made to document the objective progression even after discontinuation of treatment due to symptomatic deterioration. A patient is classified as having PD due to “symptomatic deterioration” if any of the following occur that are not either related to study treatment or other medical conditions:

- Weight loss >10% of body weight.
- Worsening of tumor-related symptoms.
- Decline in performance status of >1 level on ECOG scale.

12.0 Descriptive Factors

None

13.0 Treatment/Follow-up Decision at Evaluation of Patient

- 13.1 Patients who have not had disease progression and have experienced acceptable toxicity are to continue treatment per protocol or a maximum of 2 years (approximately 35 cycles) or until confirmed PD, unacceptable toxicity or refusal.
- 13.2 The first instance in which a patient's disease status meets the RECIST criteria for PD will continue for two additional cycles of treatment per protocol (approximately 6 weeks) and then undergo a disease evaluation. If the initial documented progression is not confirmed by this scan, patients will continue treatment per protocol. If the initial documented progression is confirmed by this scan, patients will go to the event-monitoring phase until death or a maximum of years post-registration.

Exception: Patients who develop PD in the CNS only should discontinue study treatment and go to Event Monitoring.

- 13.3 Criteria for discontinuation of protocol therapy include:
- Disease progression where disease progression is: the development of a new metastatic lesion or an objective status of disease progression (as defined by RECIST criteria) on two consecutive evaluations at least 6 weeks apart (section 13.2). ***Exception: Patients who develop PD in the CNS only should discontinue study treatment and go to Event Monitoring.***
 - Request by patient to discontinue study treatment
 - Unacceptable toxicity
 - Intercurrent illness that would, in the judgment of the investigator, affect assessments of clinical status to a significant degree or require discontinuation of drug
 - Administration of radiotherapy, non-protocol chemotherapy, immunotherapy, biological agents, or an experimental drug during the trial
 - Development of new primary cancer
 - Ineligibility

Patients who discontinue treatment due to intolerability, patient request, physician decision, or inter-current illness preventing further administration of protocol treatment will proceed to event monitoring phase of the trial where patient and disease status until death or a maximum of 3 years post-registration

- 13.4 Patients who complete 2 years of protocol treatment (approximately 35 cycles) without (confirmed) disease progression will proceed to the Observation phase until confirmed disease progression or a maximum of 3 years post registration. If the patient has a documented confirmed disease progression during observation, the patient will continue on to the event monitoring phase for a maximum of 3 years post registration.
- 13.5 A patient is deemed ineligible if after registration, it is determined that at the time of registration, the patient did not satisfy each and every eligibility criteria for study entry.
- If the patient received any protocol treatment, all data (except biospecimens) up until the point of confirmation of ineligibility must be submitted. Event monitoring will be required per Section 18.0 of the protocol.

- If the patient never received any protocol treatment, on-study material (except biospecimens) and the End of Active Treatment/Cancel Notification Form must be submitted. No further data submission is necessary.

13.6 A patient who withdraws consent before any study treatment is given. On-study material (except biospecimens) and the End of Active Treatment/Cancel Notification Form must be submitted. No further data submission is necessary.

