4.0 Test Schedule

Tests and Procedures	≤28 Days prior to Registration	Day 1 (+/-3 days) of each cycle	End of Treatment	Observation	
				Every 12 (+/- 2) weeks for months 24 thru 36 post registration	at progression
History and Physical Examination, wt, PS	X	X	X	X	X
Height	X				
Adverse Events Assessment	X	X	X	X	X
Pregnancy Test – Urine or Serum –HCG ¹		X ⁶			
CBC w/diff	X ²	X	X	X	X
Renal Profile: Sodium, Potassium, Chloride, Bicarbonate, Creatinine, Bun, Glucose	X ²	X	X	X	X
Albumin, bilirubin total and direct, alkaline phosphatase, total protein, AST, and ALT	X ²	X			
FT4 and TSH	X	X	X		
Disease Evaluation ³	X	X ⁴	X	X	X
Research Tissue Collection ^R		X ⁵			
Photograph of lesions	X	X	X	X	X

1. For women of childbearing potential only. Must be done ≤72 hours prior to registration.

2. ≤14 Days prior to Registration

3. Radiographic tumor imaging assessments must include CT scan, PET/CT, or MRI of the chest, abdomen, and pelvis. CT scan or MRI of the brain with contrast will only be performed if symptoms or signs of CNS metastasis are present. Use same imaging throughout the study.

4. At the completion of cycle 4 (approximately week 12) and then at completion of every 4th cycle (approximately every 12 weeks) thereafter (±7days) until PD.

5. Tissue specimens must be collected and submitted after registration but prior to the start of treatment, at completion of cycles 2 and 4 (approximately weeks 6 and 12).

6. For women of childbearing potential only. Must be done ≤ 72 hours prior to start of treatment. Must be repeated if pre-registration test is > 72 hours prior to the start of treatment.

R Research funded (see Section 19.0)

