9.5 General patient monitoring and supportive care guidelines

9.51 Patients should be carefully monitored during the treatment phase and then followed appropriately. Decisions for retreatment or dose modifications/interruption should follow the guidelines in Sections 8.2.

9.52 Patients who have an ongoing study agent-related serious adverse event upon study completion or at discontinuation from the study will be contacted by the treating physician or his/her designee at least every 2 weeks until the event is resolved or determined to be irreversible.

- 9.6 Side effect management for **PEMBROLIZUMAB** toxicities- these are to be regarded as guidelines for managing toxicity that occurs with pembrolizumab therapy and should not replace clinical judgement (i.e. - patients with grade 1 rash may require systemic steroids).

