10.4 Expedited Reporting Requirements for IND/IDE Agents

10.41 Phase 1 and Early Phase 2 Studies: Expedited Reporting Requirements for Adverse Events that Occur on Studies under an IND/IDE within 30 Days of the Last Administration of the Investigational Agent/Intervention ^{1, 2}

FDA REPORTING REQUIREMENTS FOR SERIOUS ADVERSE EVENTS (21 CFR Part 312) NOTE: Investigators MUST immediately report to the sponsor ANY Serious Adverse Events, whether or not they are considered related to the investigational agent(s)/intervention (21 CFR 312.64) An adverse event is considered serious if it results in ANY of the following outcomes: 
 1) Death 2) A life-threatening adverse event 3) An adverse event that results in inpatient hospitalization or prolongation of existing hospitalization for ≥ 24 hours 4) A persistent or significant incapacity or substantial disruption of the ability to conduct normal life functions 5) A congenital anomaly/birth defect. 6) Important Medical Events (IME) that may not result in death, be life threatening, or require hospitalization may be considered serious when, based upon medical judgment, they may jeopardize the patient or subject and may require medical or surgical intervention to prevent one of the outcomes listed in this definition. (FDA, 21 CFR 312.32; ICH E2A and ICH E6). 		
ALL SERIOUS adverse events that meet the above criteria MUST be immediately reported to the sponsor within the timeframes detailed in the table below.		
Hospitalization	Grade 1 and Grade 2 Timeframes	Grade 3-5 Timeframes
Resulting in Hospitalization ≥24 hrs	7 Calendar Days	24-Hour 3 Calendar Days
Not resulting in Hospitalization ≥24 hrs	Not required	

Expedited AE reporting timelines are defined as:

- "24-Hour; 3 Calendar Days" - The AE must initially be reported within 24 hours of learning of the AE, followed by a complete expedited report within 3 calendar days of the initial 24-hour report.
- "7 Calendar Days" - A complete expedited report on the AE must be submitted within 7 calendar days of learning of the AE.

¹Serious adverse events that occur more than 30 days after the last administration of investigational agent/intervention and have an attribution of possible, probable, or definite require reporting as follows:

Expedited 24-hour notification followed by complete report within 3 calendar days for:

- All Grade 3, 4, and Grade 5 AEs

Expedited 7 calendar day reports for:

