15.12 Formulation

Pembrolizumab is available as a liquid 25 mg/mL, 100 mg/vial.

15.13 Preparation and storage:

Vials should be stored in the refrigerator at temperatures between 2-8°C. Drug concentrate is further diluted with normal saline (or 5% dextrose in the concentration range of 1 to 10 mg/mL) in IV containers made of polyvinyl chloride (PVC) or non-PVC material. The infusion solution in the IV bag should be immediately administered. Pembrolizumab solutions may be stored at room temperature for a cumulative period of up to 4 hours. This includes room temperature storage of reconstituted solution in vials, room temperature storage of infusion solution in the IV bag and the duration of infusion.

In addition, IV bags may be stored at 2-8 °C for up to a cumulative time of 20 hours. If refrigerated, the vials and/or IV bags should be allowed to equilibrate to room temperature prior to subsequent use.

15.14 **Administration:** Pembrolizumab is administered by intravenous infusion over 30 minutes via a 0.22 micron in-line filter. The final infusion volume must be between 1 and 10 mg/mL. Maximum rate of infusion should not exceed 6.7 mL/minute through a peripheral or indwelling catheter. Flush the line with 0.9% NaCL following the completion of the infusion.

15.15 Pharmacokinetic information:

a) Absorption – during repeated dosing of MK-3475 every two weeks, steady state conditions were reached within 16 weeks of treatment. Steady state trough concentrations obtained at 24, 36 and 48-weeks of treatment

with 10 mg/kg Q2W were on average 20% percent higher compared to 10 mg/kg Q3W treatment.

b) Distribution – pembrolizumab has a limited volume of distribution.

c) Excretion – mean estimated $t_{1/2}$ values from the 28-day single dose profiles ranged from 14.1 to 21.6 days. Clearance is nonlinear and saturable.

15.16 **Potential Drug Interactions:** There are no known significant drug interactions.

15.17 **Known potential toxicities:**

Common known potential toxicities, >10%:

Cardiovascular: Peripheral edema

Central nervous system: Fatigue, headache, chills, insomnia, dizziness

Dermatologic: Pruritus, skin rash, vitiligo

Endocrine & metabolic: Hyperglycemia, hyponatremia, hypoalbuminemia, hypertriglyceridemia, hypocalcemia

Gastrointestinal: Nausea, decreased appetite, constipation, diarrhea, vomiting, abdominal pain

Hematologic & oncologic: Anemia

Hepatic: Increased serum AST

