Neuromuscular & skeletal: Arthralgia, limb pain, myalgia, back pain

Respiratory: Cough, dyspnea, upper respiratory tract infection

Miscellaneous: Fever

Less common known potential toxicities, 1% - 10%:

Dermatologic: Cellulitis

Endocrine & metabolic: Hypothyroidism, hyperthyroidism

Gastrointestinal: Colitis

Infection: Sepsis

Renal: Renal Failure

Respiratory: Pneumonitis, pneumonia

Rare known potential toxicities, <1% (Limited to important or life-threatening):

Adrenocortical insufficiency (immune-mediated), arthritis (immune-mediated), exfoliative dermatitis (immune-mediated), hemolytic anemia (immune-mediated), hepatitis (including autoimmune hepatitis; grade 4: <1%), hypophysitis (grade 2: <1%; grade 4: <1%), interstitial nephritis (with renal failure; grade 3: <1%; grade 4: <1%), Lambert-Eaton syndrome (immune-mediated), myositis (immune-mediated), nephritis (grade 2 autoimmune: <1%), optic neuritis (immune-mediated), pancreatitis (immune-mediated), partial epilepsy (immune-mediated; in a patient with inflammatory foci in brain parenchyma), rhabdomyolysis (immune-mediated), uveitis (immune-mediated)

15.18 **Drug procurement:** Pembrolizumab will be provided free of charge to study participants by Merck.

15.19 **Nursing Guidelines:**

15.191 Pembrolizumab side effects vary greatly from those of traditional chemotherapy and can vary in severity from mild to life threatening.

Instruct patients to report any side effects to the study team immediately. Side effects may be immediate or delayed up to months after discontinuation of therapy. Most side effects are reversible with prompt intervention of corticosteroids.

- 15.192 Diarrhea can be seen however, is less common than that seen with anti-CTLA-4 agents. However it can be severe, leading to colonic perforation. Instruct patients to report ANY increase in the number of stools and/or change in baseline, blood in the stool, abdominal pain to the study team immediately.
- 15.193 Rash/pruritis/dermatitis is seen. Patients should report any rash to the study team. Treat per [Section 9.0](#) and monitor for effectiveness.
- 15.194 Monitor LFT's closely as elevations in these levels could indicate early onset autoimmune hepatitis. Patients should also be instructed to report any jaundice, or right upper quadrant pain to the study team immediately.

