16.61 Safety Stopping rules

After every 5th patient has been enrolled, the tolerability of the regimen will be examined. If 2 out of the first 5 patients enrolled or more than 25% of the patients thereafter develop a grade 4 adverse event anything during the course of treatment that is considered possibly, probably, or definitely related to treatment,

enrollment will temporarily close. The study team will review all adverse event data. A trial recommendation will be formulated and presented to the MCCC DSMB – the study may permanently close or may re-open to accrual after MCCC DSMB review and IRB approval of protocol/consent form modifications.

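### Patients who stop treatment early have no scheduled adverse event assessment after End of Treatment, so finding new late events in them depends on passive reporting

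*Combined protocol and SAP*

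**What the plan says.** All references are to the combined protocol and SAP.

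- **Routing.** 13.3: "Patients who discontinue treatment due to intolerability, patient request, physician decision, or inter-current illness preventing further administration of protocol treatment will proceed to event monitoring". 13.2 does the same for progression: "If the initial documented progression is confirmed by this scan, patients will go to the event-monitoring phase". Under 13.4, Observation is reserved for patients who reach two years of treatment with no confirmed progression.
- **Scheduled assessment.** The Test Schedule (4.0) marks adverse event assessment before registration, on day 1 of each cycle, at End of Treatment, and in the two Observation columns. One of these is headed "Every 12 (+/- 2) weeks for months 24 thru 36 post registration"; the other is the visit at progression. The table in 4.1 has six-monthly contacts before and after progression, plus entries for progression, death and new primary. It lists no adverse event item.
- **Delayed effects.** 15.191: "Side effects may be immediate or delayed up to months after discontinuation of therapy".
- **Provisions for late events.** The 10.41 expedited table covers serious events "within 30 Days of the Last Administration of the Investigational Agent/Intervention". Its first footnote extends expedited reporting to later serious events judged at least possibly related. 10.52 and 10.6232 do the same for deaths. 9.52 reads "Patients who have an ongoing study agent-related serious adverse event upon study completion or at discontinuation from the study will be contacted", at least every two weeks until resolved or irreversible. 10.7 leaves the submission of late events to the Forms Packet or data entry screens.
- **Analysis.** 16.31 reports the proportion of patients with a severe level of each toxicity and gives no time window. 16.61 counts patients who "develop a grade 4 adverse event anything during the course of treatment" with at least possible attribution.

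**The concern.** Safety is part of the primary goal (2.1). The intensity of adverse event follow-up after treatment depends on how treatment ended. Patients who got through two years are examined on a schedule. Those who stopped for intolerability, by choice, for illness or for progression are not, although the protocol itself warns of delayed effects.

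The trial has one arm, and under 16.1 every eligible, consented patient who began treatment is evaluable. The denominator of each toxicity proportion is therefore fixed, and an event that is not found can only lower the numerator. The result would be set against the 10% to 13% serious event rate expected in 1.9c12, and any shortfall would look like good tolerability.

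**Working it through.** **1. The plan's own precision figure.** 16.1 gives 25.9% as the one-sided 95% upper bound for 0 responses in 10. The exact bound is 1 − 0.05^(1/10) = 0.2589, so the figure is reproduced. The point does not depend on it, but the same calculation shows what one event is worth in a toxicity proportion.

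**2. Scheduled adverse event assessments after End of Treatment (4.0, 4.1, 13.2 to 13.4).**

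| Patient | Phase | Scheduled adverse event assessments | Other scheduled contacts |
|---|---|---|---|
| Completes two years, progression-free to month 36 | Observation | 52 weeks / 12 = 4.3, about 4 | – |
| Stops at month 3 | Event monitoring | 0 | (36 − 3)/6 = 5.5, so 5 |
| Stops at month 6 | Event monitoring | 0 | (36 − 6)/6 = 5 |
| Stops at month 12 | Event monitoring | 0 | (36 − 12)/6 = 4 |
| Stops at month 18 | Event monitoring | 0 | (36 − 18)/6 = 3 |

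Contact with early stoppers is scheduled, three to five times in these examples. What is absent is a listed adverse event item at those contacts. With six-monthly spacing, the first contact may also fall well after a delayed event has begun.

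**3. What the other provisions reach.**

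- Late related serious events and deaths: reportable with no end date (10.41 footnote 1, 10.52, 10.6232), but only once someone learns of them.
- Related serious events already ongoing at discontinuation: actively followed (9.52).
- New non-serious events, such as a grade 2 or 3 immune-related event without hospitalization or a laboratory change: 10.621 and 10.622 require submission with no stated cut-off. No scheduled assessment would bring them to light in an early stopper.

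**4. Effect of one event.** Exact one-sided 95% upper bounds with n = 10 are 25.9% for 0/10 and 39.4% for 1/10. One event found or not found moves the bound by 39.4 − 25.9 = 13.5 percentage points.

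**5. Illustration with assumed inputs.** The documents give neither an early-stopping rate nor a late-event rate. For k early stoppers, each with probability q of a late severe event, P(at least one) = 1 − (1 − q)^k.

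| k of 10 | q = 5% | q = 13% |
|---|---|---|
| 3 | 14% | 34% |
| 5 | 23% | 50% |
| 7 | 30% | 62% |

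The upper q equals the top of the overall serious event rate in 1.9c12, so it is generous for late events alone. These are chances that such an event occurs, not that it goes unrecorded.

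**6. The pause rule.** Take one related grade 4 event on treatment among the first 5 patients, and a second in another of those patients that starts after the last dose. Read literally, 16.61 counts 1 of 5 and does not pause enrollment. Counting both gives 2 of 5 and does.

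**The case against.** The strongest reply is that the protocol does provide for late events. Related serious events and deaths after 30 days must be reported, 10.62 has no time limit, patients are told in 15.191 to report side effects, and 10.7 is devoted to late-occurring events. The Forms Packet named there, and the data submission table named in 18.2, are not among the documents. The event-monitoring form may already ask about adverse events. This stands, and it limits confidence to moderate. It does not remove the point: these are duties to report what becomes known, and neither 4.0 nor 4.1 schedules an assessment at which it would become known.

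Several stronger readings are tempting but unsupported:

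- *Late toxicity is missed.* Serious related events and deaths remain reportable, and 9.52 gives two-weekly contact for ongoing related serious events, the closest follow-up in the protocol. Only possible under-ascertainment can be claimed, mainly of non-serious events.
- *The unfollowed patients are those at highest risk.* That is plausible for patients who stop for toxicity, but the documents do not say it. The group also includes refusals, illness and progression.
- *An event that forces discontinuation, such as grade 3 AST, is under-counted.* 16.31 counts it at onset, and following it to resolution does not change the proportion.
- *Most of the 10 patients will be affected.* The documents give no completion rate, and response rates are not a substitute.
- *Residual drug sizes the problem.* Half-lives in 15.15 "ranged from 14.1 to 21.6 days", but that section also calls clearance nonlinear, and drug remaining is not a toxicity rate.
- *Late grade 4 events cannot come to attention.* Those reported can appear in the six-monthly adverse event reports to the DSMB under 16.6. What they would not do, on a literal reading, is trigger the pause.

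A contact at about 30 days may also overlap with existing work. The timing of the End of Treatment visit is not given, and the main reporting period for serious events already runs to 30 days.

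**Conclusion.** The point holds as a gap in active ascertainment. After End of Treatment an early stopper has no scheduled adverse event assessment, against up to about 4 for a progression-free completer. New late events in early stoppers are therefore found by passive reporting, and non-serious grade 2 to 3 immune-related events and laboratory changes may be under-counted. The direction is known: any loss makes the combination look safer. The size is not known, because the documents give no late-event or early-stopping rate. With 10 patients a single event is worth 13.5 percentage points on the upper bound. Separately, 16.61 read literally leaves out related grade 4 events that start after the last dose, and 16.31 has no window.

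Confidence is moderate. The conclusion assumes that the Forms Packet and data submission table add no adverse event question at event-monitoring contacts, which cannot be checked. In a descriptive pilot this does not undermine the design, but it is worth correcting because safety is a primary aim and the remedy is cheap.

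**What to change.** 1. In 4.0 and 4.1, add an adverse event assessment for every patient who stops pembrolizumab for any reason, at about 30 days and again at about 90 to 120 days after the last dose. Telephone is enough, though it will pick up laboratory changes only where tests were done in routine care. If the End of Treatment visit already falls near 30 days, it can serve as the earlier contact. The later time is close to the 12-week and 120-day periods the protocol uses for other purposes.
2. Add an adverse event question to the existing six-monthly event-monitoring contacts.
3. Reconcile 4.0, 4.1, 9.52, 10.7 and 13.3 so that they describe the same follow-up, and state in the protocol what the Forms Packet requires for late events.
4. Define one adverse event window, from first dose through the end of this follow-up, and use it for both the 16.31 summary and the 16.61 count.

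Cost: a protocol amendment, two brief contacts for at most 10 patients by existing staff, and a little more data entry. The reported toxicity rate may come out somewhat less favourable.
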